Title	ICER Observational RWE Pilot: Hereditary Angioedema (HAE)	
Protocol version and date	V 2.0, 12 April 2021	
Protocol registration or comment period	Manufacturer comment period took place between 5 March 21 through 25 March 21	
Study type	Observational study	
Objective	To describe baseline demographic characteristics, attack rates, and attack-related medical service utilization among initiators of three HAE treatments for prophylaxis use (Takhzyro, Haegarda, Cinryze).	
Country(-ies) of study	United States	
Data source	Optum’s De-identified Clinformatics® Data Mart	
Protocol contributors/ project team	[name] Scientific Partnerships Lead Aetion, Inc.	[name], MS Sr Principal Product Scientist Aetion, Inc.
	[name] Scientist Aetion, Inc	[name], MS Senior Vice President, Health Economics Institute of Clinical and Economic Review
	[name], MS Sr. Research Scientist, Department of Pharmacy University of Washington	[name], MPH Associate Professor, Department of Pharmacy University of Washington

The study will be conducted in compliance with the protocol and any applicable regulatory requirements.

Throughout this document, symbols indicating proprietary names (®, TM) may not be displayed. Hence, the appearance of product names without these symbols does not imply that these names are not protected.

1. Table of contents

1.	Table of contents	2
2.	List of abbreviations	3
3.	Rationale and background	3
4.	Research questions and objectives	4
5.	Research methods	5
5.1.1.1	Study population	5
5.1.1.2	Prophylaxis initiation cohort for evaluating	5
5.1.1.3	Follow-up cohort for evaluating the exploratory research objective	6
5.1.1.4	Dose reduction cohort evaluating the exploratory research objective	6
5.2	Variables	7
5.2.1.1	Patient characteristics	7
5.2.1.2	Treatment	8
5.2.1.3	Outcome definitions	8
5.2.1.4	HAE attack rates	8
5.2.1.5	Costs associated with HAE attacks	9
5.2.1.6	Costs during baseline	10
5.2.1.7	Utilization	10
5.2.1.8	Hospitalization utilization	10
5.3	Data sources	11
5.3.1.1	Optum's De-identified Clinformatics® Data Mart	11
5.3.1.2	General notes on administrative databases	11
5.4	Statistical analysis	11
5.4.1.1	Baseline attack rates (primary objective)	11
5.4.1.2	Baseline costs (primary objective)	12
5.4.1.3	Exploratory Follow- up descriptive analyses	12
5.4.1.4	Sensitivity analyses	12
5.4.1.5	Limitations	13

5.4.1.6	Software	13
6.	References	14
	Annex 1: HAE drugs	17
	Annex 2: Variable definitions and code lists	22
	Annex 3: Results Table Shells	27
	Annex 4: United Healthcare HAE Drug Coverage Policies	30

2. List of abbreviations

AEP	Action Evidence Platform®
ED	Emergency department
EHR	Electronic health records
FDA	Food and Drug Administration
HAE	Hereditary angioedema
HIPAA	Health Insurance Portability and Accountability Act
HTA	Health technology assessment
ICER	Institute for Clinical and Economic Review
IU	International unit
Kg	Kilogram
RCT	Randomized controlled trial
RWE	Real-world evidence
Rx	Prescriptions

3. Rationale and background

Drugs that receive accelerated approval through the FDA often have uncertainties in clinical and cost-effectiveness at time of launch and subsequent health technology assessment (HTA). ICER is piloting a process to reassess drugs, approved under accelerated pathways, 24 months after its initial assessment. The ICER reassessment will focus on using real-world evidence (RWE) to address uncertainties and update its initial clinical review and cost-effectiveness modeling.

A series of analyses using the Action Evidence Platform® (AEP) will be conducted within the Optum's de-identified Clinformatics® Data Mart Database to inform the RWE reassessment.

Results from this analysis and supplemented literature will be used by the University of Washington to provide updated inputs to the original HAE cost-effectiveness model.

4. Research questions and objectives

In the original [ICER HAE report](#), published in November 2018, a number of uncertainties were noted that could substantially impact the cost-effectiveness of the three therapies reviewed:

- Key cost-effectiveness model assumptions were based on data from RCTs (e.g., patients' baseline HAE attack rates), however, 'minor adjustments in key assumptions (e.g., frequency of attacks) could result in substantially different cost-effectiveness results.' How does real-world clinical practice align with the model assumptions derived from the RCTs?
- The FDA label for Takhzyro suggests that patients who remain attack-free for six months may be considered for less-frequent dosing (i.e., one dose every four weeks instead of every two weeks). However, the real-world proportion of patients who will switch to – and remain on – the less-frequent dose is unknown. Less frequent dosing could impact the incremental cost-effectiveness.
- Health care resource utilization and cost inputs were used from published observational studies that were published up to 10 years ago. Revising these estimates with updated RWE could impact the drugs' cost-effectiveness.

The objectives of this observational RWE study are focused on addressing these uncertainties and generating updated cost-effectiveness model inputs. The following research objectives will be addressed:

Primary Objective. Describe baseline demographic characteristics, attack rates, and attack-related medical service utilization among initiators of one of the three treatments for long-term prophylaxis use (Takhzyro, Haegarda, or Cinryze).

- What is the HAE baseline attack rate per month (stratified by severity) in the six months pre-initiation?
- Where is on-demand treatment for acute attacks administered? What is the distribution of specific drugs? How many prescriptions do patients receive?
- For patients with severe attacks, what percent end up hospitalized, and within these patients, what is the utilization of procedures such as cricothyrotomy/tracheotomy, intubation, and artificial respiration?
- What are the costs associated with medical utilization during the acute attack?

Exploratory Objective: Explore attack rates and utilization following long-term prophylaxis initiation.

- What is the severe attack rate per month, post-initiation?
- What percent of patients are attack-free during the follow up period?

- What are the utilization patterns of the prophylactic medications, post initiation?
- What percent of patients receive less frequent dosing for Takhzyro after six months attack free (in line with FDA recommendations)? Do any patients titrate down prior to six months?

5. Research methods

5.1.1.1 Study population

The analysis is specifically focused on patients who are eligible for prophylaxis therapy in line with the target population in the ICER assessment.

5.1.1.2 Prophylaxis initiation cohort for evaluation

[figure not shown]
Patients will be eligible to enter the cohort on initiation of Takhzyro, Haegarda, or Cinryze as a prophylactic treatment during October 10, 2008 through October 3rd, 2019 (Figure 1). October 2008 was selected as the start of the study period based on the approval date for Cinryze, the earliest of the medications to be approved. Clinical experts confirmed that 2008 reflects the current treatment paradigm of medications targeting the BK pathway and that all new treatments after 2008 reflect a continual shift away from inferior anabolic androgen therapies. The study period was also selected to maximize sample size for this rare disease.

New use will be defined as no use of Takhzyro or Haegarda, during the 180 days prior (washout period), and no use of Cinryze as a prophylactic treatment during this 180-day washout period. Because Cinryze is used for both acute attacks (off label) and prophylaxis, patients will be excluded based on evidence of prophylactic use of Cinryze (see definition in Annex 2) during the 180 days prior to cohort entry and will be required to have continuous enrollment and evidence of recurring use during the 90 days following cohort entry. Patients receiving other prophylactic treatments (see Annex 1) during the baseline period will also be excluded. Each patient will be included only once, on the first qualifying event. Patients will be required to have at least 180 days of enrollment prior to cohort entry to obtain baseline attack rates.

Using this cohort, we will evaluate baseline outcomes. Patients' demographic characteristics will be assessed at cohort entry. Patients' attack rates, and attack-related medical service utilization and costs will be evaluated.

Note: HAE does not have specific ICD9/10 diagnostic codes. We used initiation of HAE specific treatment to identify patients of interest (i.e., patients with HAE). The method of using HAE treatments to identify HAE patients has been used widely in the literature (Tachdjian 2020, Banerji 2020, [Vande Walle 2018](#)).¹⁻³ In addition, there is no indication that HAE treatments are used off-label for non-HAE patients.

Figure 1: Prophylaxis initiation cohort study design diagram

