5.2.1.4 HAE attack rates

Observational studies that evaluate attack rates in claims or EHR data sets are limited. There is currently no validated method to evaluate HAE attacks in claims data.

In creating our definitions of severe and non-severe attacks, we took guidance from clinical experts, treatment guidelines, and published literature that identified symptoms ([Longhurst & Bork 2019](#))⁵ or used diagnoses codes indicative of an attack (Tachdjian 2020).¹ Symptoms and diagnoses codes were cross referenced in a de novo code search to capture both ICD-9 and ICD-10 codes.

Attacks are defined by severity:

- **Severe attack:** Treatment guidelines and empirical data suggest that severe attacks are typically treated in the ED.⁶ For this analysis, severe attack will be defined in two ways: broadly as all-cause ED visits with or without hospitalization and more specifically as HAE ED visits with or without hospitalization. HAE specific severe attacks will be defined by a claim for an ED visit with or without hospitalization that includes diagnoses and drugs indicative of an attack (see Annex 2).
- **Non-severe attack-** Non-severe attacks are treated with on-demand therapy either by self-administration or administration by a healthcare professional. An attack treated by a healthcare professional will be defined as a medical service claim for an on-demand therapy occurring outside an inpatient or ED setting (e.g., physician office). For self-administration, we will estimate the number of attacks treated by calculating the number of doses dispensed based on dispensed quantity and approved dosages. Based on [treatment guidelines](#),⁶ patients should readily have on-demand therapy to treat two attacks, thus we will consider any doses dispensed over the two on-hand dosages of on-demand therapy as evidence of an attack.

Data on the duration of attacks by severity is limited, however attacks generally last between two and five days.⁷ Thus, on-demand therapy administrations by a healthcare professional, ED visits, and inpatient hospitalizations occurring within five days of each other will be considered part of a single attack. In cases where an on-demand therapy administration occurs within five days of an ED visit or hospitalization, the attack will be counted as a severe attack.

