5.3.1.1 Optum's De-identified Clinformatics® Data Mart

Optum's Clinformatics® Data Mart (CDM) is derived from a database of administrative health claims for members of large commercial and Medicare Advantage health plans. The database includes approximately 17-19 million annual covered lives, for a total of over 65 million unique lives over a 9-year period (1/2007 through 12/2019). Clinformatics® Data Mart is statistically de-identified under the Expert Determination method consistent with HIPAA and managed according to Optum® customer data use agreements.^{8,9} CDM administrative claims submitted for payment by providers and pharmacies are verified, adjudicated and de-identified prior to inclusion. This data, including patient-level enrollment information, is derived from claims submitted for all medical and pharmacy health care services with information related to health care costs and resource utilization. The population is geographically diverse, spanning all 50 states.

There are 67,691,644 total patients in the data with events spanned January 1, 2007 through March 31, 2020.

Please see Annex 4 for HAE drug coverage policies for United Healthcare.

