5.4 Statistical analysis

5.4.1.1 Baseline attack rates (primary objective)

Attack rates will be calculated as the total number of attacks in the cohort divided by the number of person-months during baseline (six months prior to initiation of prophylaxis treatment). The rates

and percentages of attacks by severity (severe all-cause, severe-HAE specific, non-severe) will also be calculated for the baseline cohort.

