Annex 3: Results Table Shells

Table 1: Baseline characteristics of patients with HAE

Characteristic	RWE results	Notes	Prior ICER review base case	Prior ICER review source
Mean age			39.63	Banerji et al. 2017, ³⁰ Longhurst et al. 2017, ³¹ Zuraw et al. 2010 ³²
Female, %			68.4%	Banerji et al. 2017, ³⁰ Longhurst et al. 2017, ³¹ Zuraw et al. 2010 ³²
Mean weight, females			76.4	Fryar et al. 2016 ³³
Mean weight, males			88.8	Fryar et al. 2016 ³³
List of top 10 non-HAE therapies (therapeutic class)				

Table 2: Attack rates, utilization, and costs in the six-month baseline period before initiation of prophylaxis treatment

Characteristic	RWE results	Notes	Prior ICER review base case	Prior ICER review source
ATTACK RATES AND TREATMENTS ADMINISTERED				
Mean attack rate per month (HAE-specific severe and non-severe)			3.39	Banerji et al. 2017, ³⁰ Longhurst et al. 2017, ³¹ Zuraw et al. 2010 ³²
Number of patients who are attack free in baseline period before starting prophylaxis therapy		Due to drug indications and health plan requirements, this is expected to be minimal or 0.	-	

Distribution of severe attack free months			-	
Proportion of attacks, by severity				
Severe - HAE specific			-	
Severe - All-cause			-	
Non-severe			-	
Treatment administered – Non-severe attacks				
Self			64.9%	Riedl et al, 2015 ³⁴
Home nurse			13.8%	Riedl et al, 2015 ³⁴
Outpatient			21.3%	Riedl et al, 2015 ³⁴
% of severe-HAE specific attacks resulting in hospitalization			40.9%	Zilberberg et al 2011a ³⁵
% of hospitalized patients receiving cricothyrotomy/tracheotomy			40.0%	Bork et al ³⁶
% of cricothyrotomy/tracheotomy patients who receive artificial respiration			40.0%	Bork et al ³⁶
% of hospitalized patients who are intubated			60.0%	Bork et al ³⁶
% of intubated who receive artificial respiration			26.7%	Bork et al ³⁶
% of attacks treated with these on-demand drugs				Assumption in model
Berinert			25%	
Kalbitor			25%	

Firazyr			25%	
Ruconest			25%	
BASELINE HAE-SPECIFIC COST OUTCOMES				
Costs per home nurse			\$179	Graham et al 2017 ³⁷
Costs per physician office visit			\$266	Graham et al 2017 ³⁷
Costs per ED visit			\$1,796	Zilberberg et al 2011a and 2011b ^{35,38}
Costs per hospitalization			\$5,782	Zilberberg et al 2011a and 2011b ^{35,38}
BASELINE HAE-SPECIFIC UTILIZATION OUTCOMES				
Average number of home visits			-	
Average number physician office visits			-	
Average number of ED visits			-	
Average number of hospitalizations			-	

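### The primary attack rate pools baseline time back to 13 April 2008, but the protocol does not establish that the on-demand drugs that reveal non-severe attacks were claimable throughout

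*Protocol*

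**What the plan says.** **Entry window.** Section 5.1.1.2 admits patients who start one of the three prophylactic drugs "during October 10, 2008 through October 3rd, 2019". Its reason for the start date is that "October 2008 was selected as the start of the study period based on the approval date for Cinryze, the earliest of the medications to be" licensed. It adds that clinical experts regard 2008 as reflecting the current treatment paradigm, and that the period was chosen to maximize the sample in a rare disease. On-demand products play no part in the choice.

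**Look-back.** The same section says "Patients will be required to have at least 180 days of enrollment prior to cohort entry to obtain baseline attack rates". Section 5.3.1.1 describes data with "events spanned January 1, 2007 through March 31, 2020", so baselines in 2008 can be observed.

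**How a non-severe attack is found.** Section 5.2.1.4 states: "Non-severe attacks are treated with on-demand therapy either by self-administration or administration by a healthcare professional". An attack treated by a professional "will be defined as a medical service claim for an on-demand therapy occurring outside an inpatient or ED setting". Self-treated attacks are derived from dispensed on-demand doses beyond two held in reserve. Severe attacks are found differently: under Annex 2, an emergency or inpatient claim can qualify on a diagnosis alone.

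**The estimator.** Section 5.4.1.1: "Attack rates will be calculated as the total number of attacks in the cohort divided by the number of person-months during baseline". There is no calendar stratum. The attack-rate sensitivity analyses in section 5.4.1.4 vary the episode window and the two-dose deduction, not the period. A restriction to 2017–2020 is planned for costs only, if sample size allows (sections 5.2.1.5, 5.2.1.6 and 5.4.1.2).

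**Drug mix.** Annex 3, Table 2 reports the percentage "of attacks treated with these on-demand drugs" for Berinert, Kalbitor, Firazyr and Ruconest, beside a prior assumption of 25% each.

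**The concern.** The start date comes from a drug that defines who enters the cohort. The primary outcome depends on other drugs. If no on-demand product could be claimed for part of the baseline period, non-severe attacks in that time cannot appear in the numerator, while the person-months still count in the denominator. Severe attacks would still be counted, so the loss falls on one component only.

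Three Table 2 outputs would move:
- The non-severe and total rates would be too low.
- The severe share would be too high.
- The drug mix would under-represent any product that became claimable later than the others.

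This matters because the total rate is to be compared with the 3.39 attacks per month of the earlier model. Section 4 of the protocol warns that modest changes in attack frequency could alter the cost-effectiveness results substantially. No planned analysis would reveal the problem, and the limitations in section 5.4.1.5 do not mention product availability over time.

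**Working it through.** The protocol gives no expected rate, sample size or entry count by year, so there is no planned figure to reproduce. The check is date arithmetic plus a dilution formula.

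**Inputs from the protocol**
- Entry from 10 October 2008 to 3 October 2019, which is 4,011 days (section 5.1.1.2).
- Baseline of 180 days (section 5.1.1.2).
- Reference rate of 3.39 per month (Annex 3, Table 2), used only as a scale.

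**Inputs assumed, because the protocol does not give them**
- *L*, the days from 10 October 2008 until an on-demand product was first claimable: 0, 365, 730 or 1,095.
- Entries spread uniformly over the 4,011 days.
- *s*, the non-severe share of true attacks: 0.5, 0.7 or 0.9.

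**Step 1: earliest baseline day.** 10 October 2008 − 180 days = 13 April 2008. This is 468 days after the data begin on 1 January 2007. Entrants before 8 April 2009 (10 October 2008 + 180 days) have some baseline time before 10 October 2008.

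**Step 2: blind share of baseline time.** Summing, over uniform entry days, the baseline days that fall before the claimable date gives

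*f* = (*L* + 90.5) / 4,011.

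For *L* = 0 this is 90.5 / 4,011 = 2.3%. For *L* = 365 it is 455.5 / 4,011 = 11.4%.

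**Step 3: effect on the rate and severity split.** If all non-severe attacks in blind time are lost,

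observed total rate = 3.39 × (1 − *f* × *s*)

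observed severe share = (1 − *s*) / (1 − *f* × *s*).

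| Claims possible from | *f* | Rate, *s* = 0.5 | Rate, *s* = 0.7 | Rate, *s* = 0.9 | Severe share, *s* = 0.7 (true 30%) |
|---|---|---|---|---|---|
| 10 Oct 2008 | 2.3% | 3.35 | 3.34 | 3.32 | 30.5% |
| + 1 year | 11.4% | 3.20 | 3.12 | 3.04 | 32.6% |
| + 2 years | 20.5% | 3.04 | 2.90 | 2.77 | 35.0% |
| + 3 years | 29.6% | 2.89 | 2.69 | 2.49 | 37.8% |

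The non-severe rate alone falls by the fraction *f*. If a product was already claimable by 13 April 2008, *f* = 0 and the rate loses nothing.

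**Step 4: why these are upper-end figures.** Sections 5.1.1.3 and 5.1.1.4 date Takhzyro's approval to 23 August 2018, so its initiators add no early baseline time. If they make up a fraction *x* of entrants and the rest enter uniformly, *f* is multiplied by (1 − *x*). In addition, an attack taken to the emergency department because no on-demand drug was at hand would still be counted, as severe. Step 3 treats it as lost.

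**The case against.** The strongest objection concerns the premise. A reader might infer that the protocol shows no on-demand drug was on the market in the earliest baselines, because it calls Cinryze the earliest to be approved. The text does not support that. The preceding sentence of section 5.1.1.2 names Takhzyro, Haegarda and Cinryze, and the phrase most naturally refers to those three. The protocol gives no approval or billing date for Berinert, Kalbitor, Firazyr or Ruconest. A flat statement that the rate is biased down would therefore need facts from outside it.

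Second, Cinryze may itself serve as on-demand therapy. Section 5.1.1.2 acknowledges off-label acute use and Annex 1 gives an acute-attack dose, although Table 2 leaves it out of the on-demand mix. If acute Cinryze claims count, detection is possible from October 2008. At most the 2.3% row then applies, and the effect on the total rate is about 1% to 2%.

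Third, the start date was a reasoned choice, with expert support and a sample-size motive. The limitations also refer to a separate Model Analysis Plan for criteria on using attack estimates in the model. That plan is not at hand and may limit the consequences.

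All of this stands, and it confines the point to a conditional one. It does not remove the point. The expert statement concerns the treatment paradigm, not whether attacks can be detected in claims. The Cinryze question is left open by the protocol. Criteria applied later in the model would not correct a denominator that contains unobservable time.

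**Conclusion.** The point holds in conditional form. The protocol shows that non-severe attacks depend wholly on on-demand claims, that baseline time runs from 13 April 2008, and that all of it enters one pooled rate without a calendar restriction or sensitivity analysis. It does not show that on-demand products were claimable throughout that time, nor that they were not.

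If blind time exists, the direction is clear: non-severe and total rates down, severe share up, later products under-represented in the mix. The size cannot be settled from the protocol. The illustrated blind share runs from about 2% to about 30%, and the reduction in the total rate from about 1% (*f* = 2.3%, *s* = 0.5) to about 27% (*f* = 29.6%, *s* = 0.9). Both ranges rest on assumed availability dates, uniform entry and an assumed non-severe share. They are upper-end for the two reasons given, though not strict bounds, since entry counts by year are unknown.

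**What to change.** 1. Obtain approval and code-effective dates for each on-demand product in Annex 2 and state them in the protocol. Annex 2 already records a code-effective date for Haegarda.
2. State whether acute Cinryze claims count as on-demand therapy for the attack definition and for the drug mix.
3. Compute the total and non-severe attack rates and the severity split only from baselines that start on or after the first date on which an on-demand product was claimable. Report the full-period rate as a sensitivity analysis.
4. Report the drug mix by calendar period, or for the recent-years subgroup (2017 on) already considered for costs.
5. Keep earlier entrants for demographics and the severe attack rate.

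The cost is a few lines of protocol text and a date filter. Some early entrants are lost from the non-severe and total rates, which matters in a rare disease. If the dates show that a product was claimable from the outset, the filter in step 3 removes nobody.
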